4.3.4. CNS ORR and CNS DOR

The CNS ORR and CNS DOR will be assessed by IRC only according to the IRC charter and will be analyzed using the same method described above for the analyses of ORR and DOR.

4.3.5. Biochemical Response

The best biochemical response (Wells 2012) for both calcitonin and CEA is defined for MTC patients as follows:

- CR: normalization of serum levels following treatment maintained for a minimum of 4 weeks
- PR: $\geq 50\%$ decrease from baseline levels maintained for a minimum of 4 weeks
- stable: between $+50\%$ and -50% change from baseline levels maintained for a minimum of 4 weeks
- progression: $\geq 50\%$ increase from baseline maintained for a minimum of 4 weeks, and
- NE: if a patient does not meet the definition of any outcome described above.

The best biochemical responses for CEA and calcitonin will be derived programmatically based on the baseline and postbaseline values according to the definitions described above.

The biochemical response rate of calcitonin or CEA is defined as the proportion of patients with a best biochemical response of CR or PR.

The point estimate of the biochemical response rate and the 2-sided 95% exact binomial CI will be presented for calcitonin and for CEA. The best biochemical response for calcitonin or CEA will be summarized descriptively to show the number and percentage of patients in each response category.

Waterfall plots will be used to depict graphically the best change of calcitonin and CEA for each patient

4.3.6. Time to Response

TTR is defined as the number of months elapsed between the date of the first dose of selpercatinib and the first documentation of objective response (CR or PR, whichever occurs earlier) that is subsequently confirmed. TTR will be calculated as follows for patients who have a BOR of confirmed CR or confirmed PR:

$$\text{TTR (months)} = (\text{Response Start Date} - \text{First Dose Date} + 1) / 30.4375$$

4.3.7. Time to Best Response

TTBR is defined as the number of months elapsed between the date of the first dose of selpercatinib and the first documentation of CR (if patient's BOR is confirmed CR) or PR (if patient's BOR is confirmed PR) that is subsequently confirmed. TTBR will be calculated as follows for patients who have a BOR of confirmed CR or confirmed PR:

$$\text{TTBR (months)} = (\text{Best Response Start Date} - \text{First Dose Date} + 1) / 30.4375$$

TTBR will be summarized descriptively in the same manner as TTR.

4.3.8. Clinical Benefit Rate

CBR will be calculated based on the proportion of patients with BOR confirmed CR, PR, or SD lasting 16 or more weeks. CBR will be measured from the date of the first dose selpercatinib until the criteria for disease progression are first met. The analysis of CBR will be based on the methods described for ORR and will be presented in the summary table of BOR and ORR.

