### **2.4 Secondary Objectives (Phase 2)**

- To assess, for each expansion cohort, the anti-tumor activity of selpercatinib by determining:  
ORR based on RECIST 1.1 or RANO, as appropriate to tumor type, as assessed by Investigator;  
Best change in tumor size from baseline as assessed by IRC and Investigator;  
Duration of response (DOR) as assessed by IRC and Investigator;  
Central nervous system (CNS) ORR based on RECIST 1.1 or RANO, as appropriate for tumor type, as assessed by IRC (for patients with brain metastases);  
CNS DOR as assessed by IRC (for patients with brain metastases);  
Time to any and best response based on RECIST 1.1 or RANO, as appropriate for tumor type, as assessed by IRC and Investigator;  
Clinical Benefit Rate (CBR) based on the proportion of patients with best overall response of complete response (CR), partial response (PR), or stable disease (SD) lasting 16 or more weeks following initiation of selpercatinib, as assessed by IRC and Investigator;  
Progression-free survival (PFS) as assessed by IRC and Investigator;  
Overall survival (OS) following initiation of selpercatinib.
- To determine the safety profile and tolerability of selpercatinib.
- To characterize the PK properties of selpercatinib.

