### **3.3 General Treatment Procedures**

Patients will receive the assigned selpercatinib dose on Cycle (C) 1 Day (D) 1 in accordance with the cohort assignment. Cycles are measured in 28-day increments and the dose limiting toxicity (DLT) observation period during Phase 1 comprises the first 28 days of treatment during C1. During this time, blood samples for drug levels will be collected and patients will be monitored for safety.

Individual patients will continue daily selpercatinib dosing until PD, unacceptable toxicity, or other reasons for treatment discontinuation, as outlined in Section 6.4. Twenty-eight days after the last dose of study drug (+7 days), all treated patients will undergo an SFU visit. Patients with documented PD may be allowed to continue selpercatinib if the patient is tolerating treatment and, in the opinion of the Investigator, the patient is deriving clinical benefit from continuing study treatment, and continuation of treatment is approved by the Sponsor.

After treatment discontinuation, LTFU will occur approximately every 3 months ( $\pm 1$  month) until the patient has withdrawn consent for further participation, is lost to follow-up, has died, or the Sponsor makes a decision to close the study. Assessments may include: subsequent anticancer therapy(ies) and survival status. LTFU may be conducted by phone. For any patient who is lost to follow-up, the study site will attempt to ascertain survival information via public database search. If survival status still cannot be ascertained, patients will be considered lost to follow-up and will be censored appropriately.

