### **6.2.4      *Dose Delays/Modifications***

Cycles are 28 days in duration regardless of dose interruption unless the dose interruption includes D1 of the next cycle in which case the next cycle will start with resumption of study drug. In this situation, disease assessments should continue to follow the original schedule.

For Phase 1 and Phase 2, toxicities such as nausea, vomiting, or diarrhea or dizziness or dehydration related to these symptoms, may be managed with increased supportive care, including hydration, electrolyte repletion, and the use of anti-emetics such as serotonin type 3 (5-HT3) antagonists and/or anti-diarrheals such as loperamide as appropriate.

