Whole blood for genomic DNA	X											
Disease assessment v	X					Every 8 weeks (±7 days) starting with C3D1 through C13D1. Every 12 weeks (±7 days) thereafter.	Every 8 weeks (±7 days) through C13D1. Every 12 weeks (±7 days) thereafter.			X w		X
Confirmatory disease assessment y						At least 4 weeks post 1 st PR	At least 4 weeks post 1 st PR					

Visit Window	Screening	Cycle 1				Cycle 2-6	Cycle 7-higher b	Intra-patient Dose Escalation		EOT c	SFU d	LTFU e
	Day -28 to Day -1	D1 ±2 Days	D8 ±2 Days	D15 ±2 Days	D22 a ±2 Days	±3 Days	±7 Days	D1 ±3 Days	D8 ±3 Days			
Telemedicine Visit z							In parallel with local visits on non-disease assessment timepoints*					
Blood sample for PK aa			X						X			
EORTC QLQ-C30 or PedsQL bb		X				±7 days of each radiologic disease assessment	±7 days of each radiologic disease assessment			X		
Selpercatinib administration												
Patient dosing diary												
Patient bowel diary (MTC only) cc		X	X	X	X	D1 of C2-C6	D1 of C7, 8, 9, etc.*			X		
Adverse events dd												
Concomitant medications ee												
Survival ff												X

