4.1.1. Definitions

Definitions of efficacy and safety analysis variables are listed in respective sections of the SAP. Other variables are listed below alphabetically:

- baseline: baseline is defined as the last value recorded for a variable prior to the patient receiving the first dose of selpercatinib
- common conventions:
 - 1 pound = 0.454 kg
 - 1 inch = 2.54 cm
 - 1 year = 365.25 days. Year is calculated as (days/365.25) and will be rounded up to 1 significant digit for purposes of presentation
 - 1 month = 30.4375 days. Month is calculated as (days/30.4375) and will be rounded up to 1 significant digit for purposes of presentation
 - dates, time, and date/time fields will be displayed in data listings in ISO 8601 formats
 - change from baseline = test value at Visit X – baseline value, and
 - percentage change from baseline = $100 \times (\text{test value at Visit X} - \text{baseline value}) / \text{baseline value}$
- Study day: Study day is calculated as assessment date/event date – first dose date + 1 day if the assessment is done on or after the first dose day. If the assessment is done prior to the first dose day, study day will be calculated as assessment date/event – first dose date.

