4.3.9. Progression-Free Survival

PFS is defined as the number of months elapsed between the date of the first dose of selpercatinib and the earliest date of documented disease progression or death (whatever the cause). Unless specified otherwise, the analytical methods described in Section 4.3.3 for DOR will be used for PFS. PFS will be calculated as follows:

$$\text{PFS (months)} = (\text{Event or Censoring Date} - \text{First Dose Date} + 1) / 30.4375$$

PFS will be right censored for patients who met one or more of the following conditions:

- no postbaseline disease assessments unless death occurred prior to the first planned assessment (in which case death will be considered a PFS event)
- subsequent anticancer therapy or cancer-related surgery in the absence of documented disease progression
- died or documented disease progression after missing 2 or more consecutively scheduled disease assessment visits
- alive and without documented disease progression on or before the data cutoff date, and
- discontinue treatment and loss to follow up.

If a patient meets more than one of these conditions, then the scenario that occurs first will be used for analysis. The event or censoring date will be determined based on the conventions listed in [Table JZLA.4.2](#).

Table JZLA.4.2. PFS Censoring Scheme

Situation	Date of Event or Censoring	Outcome
Death before first planned disease assessment	Date of death	Event
Death or disease progression between planned disease assessments	Date of death or first disease assessment showing disease progression, whichever occurs first	Event
No postbaseline disease assessments	Date of first dose of selpercatinib	Censored
Subsequent anticancer treatment started before disease progression or death (without disease progression beforehand)	Date of last evaluable disease assessment prior to start of subsequent anticancer treatment	Censored
Death or disease progression after missing 2 or more consecutively scheduled disease assessments	Date of last evaluable disease assessment visit without documentation of disease progression before the first missed visit	Censored
Alive and without disease progression	Date of last evaluable disease assessment	Censored
Discontinue treatment and loss to follow up	Date of last evaluable disease assessment	Censored

Abbreviation: PFS = progression-free survival.

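### The 16-week clinical benefit cut-off falls on the due date of the second required scan, so for patients with best response SD, progression found at that scan counts as benefit or not according to the scan day

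*SAP*

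**What the plan says.** The protocol (2.4 Secondary Objectives, Phase 2) includes in CBR patients with CR, PR or "stable disease (SD) lasting 16 or more weeks following initiation of selpercatinib". SAP 4.3.8 repeats the threshold: "CBR will be calculated based on the proportion of patients with BOR confirmed CR, PR, or SD lasting 16 or more weeks". It then fixes the clock: "CBR will be measured from the date of the first dose selpercatinib until the criteria for disease progression are first met".

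Table 7-1 of the protocol sets the scans: "Every 8 weeks (±7 days) starting with C3D1 through C13D1". Protocol 3.3 gives the cycle length: "Cycles are measured in 28-day increments". If dosing is interrupted, Protocol 6.2.4 says that "disease assessments should continue to follow the original schedule", so a dose delay does not move the week-16 scan.

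For PFS, SAP 4.3.9 dates an event between planned assessments as "Date of death or first disease assessment showing disease progression, whichever occurs first". SAP 4.1.1 has a general day-count rule, "Study day is calculated as assessment date/event date – first dose date + 1 day", and the formulas for PFS and time to response also add one day. SAP 4.3.8 gives no day-count rule for CBR.

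Neither document gives CBR a window allowance, a nominal-visit rule, or a requirement that SD be seen at the week-16 scan. SAP 4.1.2.2 deals only with unscheduled visits.

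**The concern.** SD is timed to the date progression is found, and the cut-off is the due date of a scan. Two patients with the same course, stable at week 8 and progressed at week 16, can therefore be classified differently because one was scanned a few days earlier, inside the permitted window. The patient scanned on the due date is counted as having clinical benefit although that scan shows progression and SD was last seen at week 8.

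CBR is a secondary endpoint by both IRC and investigator, and is to be shown in the same table as best response and ORR. A reader will take it as the proportion whose disease was controlled at 16 weeks. For some patients it records only that they had not progressed at week 8.

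**Working it through.** **Calendar.** With 28-day cycles, day 1 of cycle n is study day 28 × (n − 1) + 1.

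- C3D1 = 28 × 2 + 1 = day 57 (week 8).
- C5D1 = 28 × 4 + 1 = day 113, which is 112 elapsed days (week 16).
- C7D1 = 28 × 6 + 1 = day 169 (week 24).

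The threshold is 16 × 7 = 112 days. The C5D1 window is days 106 to 120, or 15 permitted days.

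| Day count for CBR | Durations in the window | PD scan scored no benefit | PD scan scored benefit |
|---|---|---|---|
| Elapsed days | 105 to 119 | days 106–112 (7 of 15) | days 113–120 (8 of 15) |
| Elapsed days + 1 | 106 to 120 | days 106–111 (6 of 15) | days 112–120 (9 of 15) |

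A progression scan on day 112 cannot be classified from the text, because it depends on the convention. In elapsed days, the week-8 window (49 to 63) and the week-24 window (161 to 175) do not reach 112, so among the required scans only the week-16 scan is affected.

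**Who is affected.** A confirmed CR or PR counts in CBR whatever the progression date. The rule decides only for patients whose best response is SD.

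**Size.** The plan states no expected CBR, so there is no figure to reproduce. Nor do the documents give the share of patients with best response SD and progression first seen at week 16. If that share were 2%, 5% or 10% (an assumption), then in a set of 83 patients it would be 2, 4 or 8 patients. Counting all of them rather than none would change CBR by 2/83 = 2.4, 4/83 = 4.8 or 8/83 = 9.6 points.

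**Illustration.** Assumptions:

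- Time to progression is exponential in patients without a confirmed response, S(t) = exp(−λt), with λ = ln 2 / (median × 30.4375).
- Scan days are uniform over each 15-day window.
- Confirmed ORR is 35%, 50% or 55%, the rates hypothesised in Protocol 8.3.
- Medians of 3.6 and 7.3 months are the ends of the PFS range that Protocol 1.1 gives for multikinase inhibitors in RET fusion-positive lung cancer. The 20-month median is a further assumption.

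Overstatement is the excess over the proportion without progression at the week-16 scan. It equals (1 − ORR) × P(progression first seen at week 16 and scan day counted).

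| Median, non-responders | No PD at week 8 | No PD at week 16 | PD first seen at week 16 | Of which counted (8 to 9 days) |
|---|---|---|---|---|
| 3.6 months | 70.2% | 49.3% | 20.9% | 11.7 to 13.1 points |
| 7.3 months | 84.0% | 70.5% | 13.5% | 7.6 to 8.5 points |
| 20 months | 93.8% | 88.0% | 5.8% | 3.3 to 3.7 points |

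Multiplying the last column by 1 − ORR gives the overstatement in points:

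| Median, non-responders | ORR 35% (× 0.65) | ORR 50% (× 0.50) | ORR 55% (× 0.45) |
|---|---|---|---|
| 3.6 months | 7.6 to 8.5 | 5.9 to 6.6 | 5.3 to 5.9 |
| 7.3 months | 4.9 to 5.5 | 3.8 to 4.2 | 3.4 to 3.8 |
| 20 months | 2.1 to 2.4 | 1.6 to 1.8 | 1.5 to 1.6 |

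**The case against.** CBR is descriptive: it has no hypothesis, power or decision rule, and best response and PFS are reported separately. Dating progression to the scan that shows it is the SAP's general convention, so PFS read at 16 weeks has the same property. What is particular to CBR is only that a fixed cut-off sits on a visit date. The size in this trial is unknown. The shorter medians come from a different drug class in lung cancer and do not describe the MTC sets. All of this stands and limits the weight of the point, but it does not make the rule classify consistently.

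A reader might infer the larger gap, about 12 to 13 points at a median of 3.6 months (49% without progression at week 16 against 61 to 62% counted). That treats every patient as dependent on the SD rule. SAP 4.3.8 counts confirmed responders regardless, and the protocol hypothesises response rates of 35% to 55%, so the documents do not support it.

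A reader might also infer that the 16-week rate requires only freedom from progression at week 8. That is too strong. It describes patients with best response SD and no intervening scan who are scanned on or after the due date. The protocol encourages a C2D1 scan and a confirmatory scan at least 4 weeks after a first response, and a scan between weeks 8 and 16 can detect progression earlier.

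Finally, any repair departs from the protocol's 16-week wording, so it is more than an edit to one SAP section.

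**Conclusion.** The point holds for patients with best response SD. Followed exactly, SAP 4.3.8 scores progression at the week-16 scan as clinical benefit on 8 or 9 of the 15 permitted days and as no benefit on the other 7 or 6, and the text does not settle which split applies. The calendar arithmetic is certain. The effect on the reported rate is not. Under the exponential and uniform-window assumptions with confirmed ORR of 35% to 55%, CBR is overstated by 5.3 to 8.5, 3.4 to 5.5 or 1.5 to 2.4 points at non-responder medians of 3.6, 7.3 or 20 months. The primary ORR, DOR and PFS are unaffected. The definition should be corrected before the final analysis, but it does not threaten the trial's main conclusions.

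**What to change.** In SAP 4.3.8, define CBR as confirmed CR or PR, or best response SD with an evaluable assessment without progression on or after study day 106, the lower edge of the week-16 window (112 − 7 = 105 elapsed days, day 106 by the SAP 4.1.1 convention). Progression at the week-16 scan is then not clinical benefit on any of the 15 permitted days, a non-progressed scan done up to a week early still qualifies, and the day-count question no longer arises.

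List this in SAP 4.7 as a change from the protocol definition. CBR by the present rule, with its day-count convention stated, can be kept as a sensitivity analysis.

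The cost is one sentence, one derivation line and the disclosure, with no new data. CBR becomes slightly less favourable, and SD seen at about 15 weeks is accepted as meeting the week-16 assessment.

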4.3.9. Progression-Free Survival

PFS is defined as the number of months elapsed between the date of the first dose of selpercatinib and the earliest date of documented disease progression or death (whatever the cause). Unless specified otherwise, the analytical methods described in Section 4.3.3 for DOR will be used for PFS. PFS will be calculated as follows:

$$\text{PFS (months)} = (\text{Event or Censoring Date} - \text{First Dose Date} + 1) / 30.4375$$

PFS will be right censored for patients who met one or more of the following conditions:

- no postbaseline disease assessments unless death occurred prior to the first planned assessment (in which case death will be considered a PFS event)
- subsequent anticancer therapy or cancer-related surgery in the absence of documented disease progression
- died or documented disease progression after missing 2 or more consecutively scheduled disease assessment visits
- alive and without documented disease progression on or before the data cutoff date, and
- discontinue treatment and loss to follow up.

If a patient meets more than one of these conditions, then the scenario that occurs first will be used for analysis. The event or censoring date will be determined based on the conventions listed in [Table JZLA.4.2](#).

Table JZLA.4.2. PFS Censoring Scheme

Situation	Date of Event or Censoring	Outcome
Death before first planned disease assessment	Date of death	Event
Death or disease progression between planned disease assessments	Date of death or first disease assessment showing disease progression, whichever occurs first	Event
No postbaseline disease assessments	Date of first dose of selpercatinib	Censored
Subsequent anticancer treatment started before disease progression or death (without disease progression beforehand)	Date of last evaluable disease assessment prior to start of subsequent anticancer treatment	Censored
Death or disease progression after missing 2 or more consecutively scheduled disease assessments	Date of last evaluable disease assessment visit without documentation of disease progression before the first missed visit	Censored
Alive and without disease progression	Date of last evaluable disease assessment	Censored
Discontinue treatment and loss to follow up	Date of last evaluable disease assessment	Censored

Abbreviation: PFS = progression-free survival.

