DOR, PFS, and OS will be summarized descriptively using the Kaplan-Meier method with 95% CIs. Median follow-up for each endpoint will be estimated according to the Kaplan-Meier estimate of potential follow-up ([Schemper and Smith 1996](#)).

For patients who meet one or more of the following conditions, DOR and PFS will be right-censored as appropriate:

- Patients with no baseline or post-baseline disease assessments unless death occurred prior to the first planned post-baseline assessment (in which case the death will be considered a PFS event)
- Patients who initiate subsequent anticancer therapy in the absence of documented PD
- Patients who die or have PD after missing 2 or more consecutively scheduled disease assessment visits
- Patients who are last known to be alive and without documented PD on or before the data cut-off date

For such patients, the progression or censoring date will be determined based on described conventions ([U.S.-Food-and-Drug-Administration 2007](#)).

Analyses of secondary and exploratory endpoints will be provided in the full SAP.

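### PFS rules give opposite outcomes for a patient with no post-baseline scan who dies between the first and second planned scans, with no stated precedence

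*SAP*

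**What the plan says.** SAP 4.3.9 runs PFS from first dose to "the earliest date of documented disease progression or death (whatever the cause"). It then lists censoring conditions. Two matter here:

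- The first is "no postbaseline disease assessments unless death occurred prior to the first planned assessment". The matching row of Table JZLA.4.2 sets the censoring date as "Date of first dose of selpercatinib".
- The third is "died or documented disease progression after missing 2 or more consecutively scheduled disease assessment visits". The table censors these patients at the last evaluable assessment before the first missed visit.

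Two other rows of the table are events dated at death: "Death before first planned disease assessment" and "Death or disease progression between planned disease assessments". The second of these also covers progression.

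Where a patient meets several of the listed conditions, the SAP applies whichever occurs first. That sentence ranks censoring conditions. It does not say whether an event row or a censoring row wins.

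Protocol 8.5.3 has the same exception, "unless death occurred prior to the first planned post-baseline assessment", but no table. It carries the censoring side only.

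**The concern.** Take a patient who misses the week-8 scan and dies at week 10. There is no post-baseline scan, and the death did not precede the first planned scan, so the first condition censors the patient at Day 1. Compare a patient scanned at week 8 who misses week 16 and dies at week 18: that death is an event. Each missed one visit, and the plan's own tolerance is fewer than two consecutive missed visits.

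The first patient's death also fits the row for deaths between planned assessments, so two programmers could code the same record in opposite ways. If the censoring row is followed, patients who were perhaps too ill to be scanned leave both the event count and the risk set at Day 1. That censoring is informative, and there is no control arm in which a similar bias might offset it.

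**Working it through.** The documents state no PFS rate, median, event count or power, so there is no figure of the plan's own to reproduce.

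**1. Schedule.** Cycles are 28 days (protocol 3.3). Scans run every 8 weeks from C3D1, ±7 days (protocol 7.3).

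- First planned scan: 1 + 2×28 = Day 57 (window Days 50–64).
- Second planned scan, C5D1: 1 + 4×28 = Day 113.

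**2. A death in a patient never scanned after baseline, by date.**

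| Day of death | Scheduled scans missed | Rule that fits | Outcome |
|---|---|---|---|
| Before about 57 | 0 | "Death before first planned disease assessment" | Event |
| About 57–112 | 1 | First censoring condition and its table row | Censored at first dose |
| About 57–112 | 1 | "Death or disease progression between planned disease assessments" | Event at death |
| About 113 on | 2 or more | "Death or disease progression after missing 2 or more consecutively scheduled disease assessments" | Censored; the last evaluable assessment is baseline |

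Only the middle interval is in conflict. Censoring at first dose gives PFS = (0 + 1)/30.4375 = 0.03 months.

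**3. Size if the censoring row is applied.** Let f be the fraction of patients in the middle interval and S(t) the PFS curve of everyone else. After those deaths:

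- deaths counted as events: (1 − f)·S(t)
- deaths censored at Day 1: S(t)
- ratio: 1/(1 − f)
- difference: f·S(t)

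The documents do not give f. Assume 0.5% to 5%, and exponential PFS in the others, so S(t) = 0.5^(t/m) with assumed median m. Then S(12) = 0.500 for m = 12, S(12) = 0.707 for m = 24, and S(6) = 0.841 for m = 24. Overstatement in percentage points:

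| Assumed f | 12-month PFS, m = 12 | 12-month PFS, m = 24 | 6-month PFS, m = 24 | Median, m = 12: censored v event (months) |
|---|---|---|---|---|
| 0.5% | 0.25 | 0.35 | 0.42 | 12.0 v 11.9 |
| 1% | 0.50 | 0.71 | 0.84 | 12.0 v 11.8 |
| 2% | 1.00 | 1.41 | 1.68 | 12.0 v 11.6 |
| 5% | 2.50 | 3.54 | 4.20 | 12.0 v 11.1 |

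Kaplan-Meier curves built for 1,000 patients, with the affected deaths spread over Days 57–112, agree. For example, with f = 5% and m = 24, 12-month PFS is 70.7% censored and 67.2% with events. The relative inflation is 1/0.995 = 1.005 to 1/0.95 = 1.053.

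**4. Before those deaths.** The smaller risk set makes the censored curve slightly lower. The largest gap in the cases run was 0.8 points at 1.5 months (m = 6, f = 5%: 84.1% v 84.9%).

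**5. Scale.** At 60% PFS, ignoring censoring, the 95% half-width is 1.96·√(0.6×0.4/n): 13.6, 8.6 and 6.1 points for n = 50, 125 and 250.

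**The case against.** The strongest reply is that the SAP makes Table JZLA.4.2 the authority for event and censoring dates, and a death at week 10 lies between the planned week-8 and week-16 scans. On its wording the table already makes that death an event. This stands against any claim that the SAP definitely censors such a patient. It does not remove the problem, because the row for no post-baseline assessment is in the same table and fits the same patient.

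The affected group is probably small. Entry requires a life expectancy of at least 3 months (protocol 4.1), a week-4 scan is encouraged, and an end-of-treatment scan is due if none was done in the last two cycles (protocol 7.3, 7.5). This largely stands, but the safeguards leave gaps. The week-4 scan is optional. Baseline imaging up to 28 days before C1D1 can mean that no end-of-treatment scan is due after a very early stop. Patients who stop for reasons other than progression are not required to have further scans. They remain in the efficacy set, because SAP 2.2 admits patients who died before reaching 6 months of potential follow-up.

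PFS is secondary and descriptive, the deaths still count in OS, and all deaths are listed (SAP 4.3.10, 4.3.11.3). This stands and limits the consequence.

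Finally, the rule is a protocol convention, and earlier SAP versions supported earlier analyses, so changing it could affect comparability. That is a reason to report the number affected and add a sensitivity analysis. It is not a reason to leave the conflict in place.

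**Conclusion.** The point holds as an unresolved conflict. For a death at about Days 57–112 in a patient with no post-baseline scan, the SAP gives both an event and censoring at first dose. If the censoring row is used, later PFS is inflated by 1/(1−f). At an assumed f of 0.5% to 5%, that is about 0.3 to 2.5 points in 12-month PFS with an assumed 12-month median, and up to about 3.5 points with an assumed 24-month median. The actual size cannot be found from the documents. In sets of 50 to 250 it would sit inside the confidence interval under these assumptions. The primary ORR analysis and the sample size are untouched.

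A reader might infer three stronger things that the documents do not support:

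- That early deaths in general drop out of PFS. Deaths before about Day 57 are expressly events.
- That the bias favours the drug at every time point. Before the affected deaths the curve is marginally lower.
- That this one condition accounts for every lost death. After two missed scans, the separate missed-visit rule censors as well.

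It should still be corrected: the SAP governs the final study report and describes no sensitivity analysis of PFS censoring.

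**What to change.** 1. In SAP 4.3.9, Table JZLA.4.2 and protocol 8.5.3, count a death with no post-baseline assessment as a PFS event at the date of death if fewer than two consecutive scheduled assessments were missed. State that this takes precedence over the row for no post-baseline assessment.
2. Report the number of such patients in each efficacy analysis set.
3. Add a sensitivity analysis counting all deaths as events. This also covers deaths after two or more missed scans. Together with the counts in item 2, it lets readers relate the result to earlier analyses that may have used the censoring row.

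Cost: a sentence and a table row in the SAP, a matching edit in the protocol, and a small amount of extra analysis. Under SAP 4.1 an analysis change needs a protocol amendment only if it alters a principal feature; otherwise it is described and justified in the study report. PFS may be slightly less favourable.
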